### Study Aims

The primary aim of our study is to evaluate the effect of a three-month peer support intervention on the clinical outcome of MetS components as compared to the control group. Furthermore, this study aims to determine the impact of the peer support intervention on dietary practices (nutrient intake, food frequency score), physical activity levels and lifestyle behaviours (smoking, alcohol consumption and sleeping habit) compared to the control group.

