## Study Sample

### Sample Size and Power Calculation

The estimated sample size based on earlier similar study (10) on one the study variables, fasting plasma glucose at 95% confidence and 80% power of an anticipated fall in FPG of 1.5 to 1.8 mmol/L. Using an equation to detect changes in a standard parallel-group trial and a 20% drop out rate, the calculated minimum required sample size is 48 participants for each group thus the totalling 96 for both randomized arm.

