### Primary Outcome – Metabolic Syndrome Biomarkers

Anthropometric measurements (body mass index, waist circumference and percentage of body fat) and blood pressure are taken during each follow-up sessions based on the WHO Protocol (27). Blood clinical outcomes will be screened using rapid finger-prick testing method; glucometer (B Braun Omnitest®3, Germany) and blood lipid profile meter (Cardiocheck® PA, Germany), as it is an accurate and sensitive method to cater a community setting intervention (28). Besides, a bio-impedance body composition analyser (InBody® H2OB Analyser, Korea) will be used to estimate fat and muscle percentage of the participants.

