### Statistical Analysis

Diet and nutrition data will be analysed using Axxya Systems Nutritionist Pro™ Diet Analysis while all statistical analyses are performed with IBM® SPSS® Statistics 23.0. Descriptive methods will be used to demonstrate to describe participant characteristics and the consistency of both groups. Independent t-test or Chi Square will be used to evaluate baseline characteristics of peer intervention

participants compared to control, overall significance of improvement across clinical outcome measures. As this is a RCT involving repeated measures, the ANOVA repeated measures model is applied to observe significant differences between and within the study groups. This includes change in clinical measures of MetS component from baseline, end of trial (3rd month) and follow up (6th month). The magnitude of change in both primary and secondary outcome measures will be estimated and the given 95% confidence intervals with the p value 0.05 was taken as the level of significance.

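### No primary endpoint, time point or success rule is named for a set of MetS biomarkers judged at a single unadjusted 0.05 level, so the false-positive rate of the primary claim is not controlled

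*Combined protocol and SAP*

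**What the plan says.** - **Aim.** Under Study Aims, the primary aim is to "evaluate the effect of a three-month peer support intervention on the clinical outcome of MetS components as compared to the control group". No component is singled out.
- **Primary outcome.** The section headed Primary Outcome describes a group of measures: "Anthropometric measurements (body mass index, waist circumference and percentage of body fat) and blood pressure are taken during each follow-up sessions", and "Blood clinical outcomes will be screened using rapid finger-prick testing method", which covers glucose and a lipid profile whose fractions are not listed. It adds fat and muscle percentage from bio-impedance.
- **Analysis.** Under Statistical Analysis, "the ANOVA repeated measures model is applied to observe significant differences between and within the study groups". The model covers "change in clinical measures of MetS component from baseline, end of trial (3rd month) and follow up (6th month". The same section mentions "overall significance of improvement across clinical outcome measures" in a sentence about t-tests and chi-square tests, without defining a global test or composite.
- **Threshold.** The section gives one level, in a sentence that covers both primary and secondary measures: "the p value 0.05 was taken as the level of significance".
- **Sizing.** Under Sample Size and Power Calculation, the calculation rests "on one the study variables, fasting plasma glucose", with 80% power, 20% dropout and 48 participants per group. Glucose has no special place in the outcome or analysis sections.

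No section gives a multiplicity adjustment, an order of testing, a composite, or a rule for how many components must improve.

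**The concern.** A confirmatory claim needs a stated criterion. Here several biomarkers share the primary label, each is measured at two times after baseline, and the analysis looks both between and within arms, all against one 0.05 threshold. Once the data are in, nothing in the plan would stop a primary claim from resting on whichever biomarker or time point fell below 0.05, even if glucose, the only variable with a power calculation, showed no difference. A reader of the results could not tell a planned finding from a selected one, and the nominal 5% would not describe the error rate of the claim.

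**Working it through.** **1. The plan's own figure.** 48 per group less 20% is 48 × 0.8 = 38.4, so about 38 completers per arm. If dropout was instead added on, 40 × 1.2 = 48 gives 40. The protocol states no SD for glucose, so 48 can be neither confirmed nor refuted. It is used below only to fix the number of completers.

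**2. Chance of at least one false positive.** Inputs:

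- Level 0.05, from Statistical Analysis. Sidedness is not stated; two-sided is assumed because 95% confidence intervals are planned.
- Number of tests k: an assumption. The MetS components are not listed by name, blood pressure could be one test or two, and the lipid fractions are not given.
- A common pairwise correlation r between test statistics: an assumption.
- One between-arm test per measure, no true effect, each test valid on its own, and any one significant result read as success.

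For independent tests the rate is 1 − (1 − 0.05)^k:

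- k = 2: 1 − 0.95² = 0.0975
- k = 5: 1 − 0.95⁵ = 0.226
- k = 6: 1 − 0.95⁶ = 0.265

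For correlated tests it is the probability that at least one of k equicorrelated standard normal statistics exceeds 1.96 in absolute value, found by numerical integration:

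| Tests | r = 0 | r = 0.5 | r = 0.9 |
|---|---|---|---|
| 2 | 9.8% | 9.1% | 7.0% |
| 5 | 22.6% | 18.3% | 10.2% |
| 6 | 26.5% | 20.7% | 10.8% |

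Every entry exceeds 5%, so the direction does not depend on the assumed count or correlation. Month 6 and within-group tests are not counted.

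**3. Power if the components are kept as co-equal primaries under Holm.** With five tests the first step is 0.05 / 5 = 0.01. Because there is no SD, the standardised difference d is back-solved: a two-sample t-test with 38 per arm has 80% power at two-sided 0.05 when d = 0.651. At 0.01, with the same d and n, power is 57.9%. Starting from 40 completers gives d = 0.634 and again about 58%. This applies to another component only if its standardised effect is the same size.

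**4. Why the secondaries need a gate.** If glucose is tested at 0.05 and a separate Holm family is tested at 0.05 whatever the glucose result, the chance of any false positive can reach about 1 − 0.95 × 0.95 = 9.75% when the two are independent. Testing the secondaries only after a significant primary holds the total at 5%, provided each test is valid.

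**The case against.** Four points can be made for the plan.

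1. **Separate testing and an any-one-counts rule are not written down.** This is correct. A reader might infer that the plan declares success on any single biomarker and so runs at a 23% error rate. The text does not say that, and the percentages above hold only under that decision rule. What stands is the omission: no rule is given, and the most permissive one is not excluded.
2. **The documents already lean toward one comparison.** Study Aims sets the effect against control, which is between arms, and Statistical Analysis labels month 3 as the end of the trial and month 6 as follow-up. A reader might infer from the reference to within-group differences that change inside the intervention arm is meant to carry the primary claim. The stated aim does not support that. This narrows the gap, but neither the comparison nor the time point is formally designated.
3. **Glucose is primary by implication.** It sizes the trial, but the sizing section calls it only one of the study variables, and the outcome and analysis sections give it no priority.
4. **This is partly a feasibility study.** Study Design and the closing discussion use that word, which lowers the weight of strict error control. However, the primary aim is effect against control, the sample is sized for 80% power, and the discussion also seeks effectiveness.

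It can also be argued that components claimed one by one need no adjustment. That is defensible if the plan says so in advance; it does not.

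**Conclusion.** The concern holds as a gap in the plan: a plural primary outcome, one unadjusted 0.05 level, and no named endpoint, time point, order, composite or success rule. Followed as written, this leaves the false-positive rate of the primary claim uncontrolled.

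The size is conditional. If any one between-arm result counted, the rate would be about 18% to 23% for five tests (correlation 0.5 to 0), 10% at correlation 0.9, and 7% to 10% for two tests. The test count, the correlations and the decision rule are assumptions, and each test is taken as valid. Confidence is high in the omission and lower in any single percentage.

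Allocation by location affects the validity of each test. It is a separate issue and is not part of these figures.

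**What to change.** Change the outcome and analysis sections as follows.

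1. State that the between-arm comparison at month 3 is primary and that within-group tests do not support the primary claim.
2. Name fasting plasma glucose as the single primary endpoint at 0.05.
3. List the other MetS components by name, from the criteria cited in Table 1, as key secondary outcomes. Test them with Holm at 0.05 only if the primary is significant. Otherwise report them as estimates with 95% confidence intervals.
4. Report month 6 and the remaining measures as estimates with 95% confidence intervals.
5. Define the phrase about overall significance across clinical measures as a named test, or delete it.

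**Cost.** Data collection and the planned 96 participants are unchanged, and multiplicity takes no power from the primary test. The claim becomes narrower than the MetS-components aim. Because the Introduction defines MetS as three or more risk factors, some participants may not have raised glucose.

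**Alternative.** If the sponsor prefers co-equal primaries, apply Holm over a named list, claim an effect only on the components that pass, and state the lower power: about 58% at the first step for five tests, with d = 0.651 declared as back-solved.

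**Timing.** The Recruitment Process section is partly in the past tense. If enrolment has begun, make the change in a dated amendment before any outcome is compared by arm. These changes control multiplicity only.

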## Discussion

PERSUADE community peer support program is intended to 'activate' a few individuals to be PL within the intervened community whom are able promote improvements on healthy nutrition and lifestyle behaviour among adults with MetS. This "activation" will eventually contribute to the prevention and management of the lifestyle-related diseases.

### Community-specific and culturally-sensitive design

PERSUADE content development is designed to be evidence-based using information gathered from a systematic review of available guidelines and published literature on prevalence and risk factors of MetS in Malaysia. Interestingly, the HBM framework allows PERSUADE to be designed as a culturally sensitive health promotion program. The framework allows PERSUADE program components to be designed in a manner that incorporated community-specific characteristics, such as beliefs, norms, values, and behaviour patterns, which shapes up the community social and environmental influences as shown in a the previous interventional model (33). Consequently, the characteristics of the community can be carefully matched with the intervention materials hence acknowledging the social and behavioural context of the target population. Additionally, a holistic understanding on how the target community perceives the severity and risk of MetS thus influence their lifestyle and health behaviours is emphasised by a qualitative analysis of focus group discussion that was recuperated as a part of PERSUADE intervention development. As a result, PERSUADE is carefully designed to address the need and acknowledge the readiness of behavioural change by reinstate the community health knowledge gap thus endowed a better module delivery method.

### Peer Empowerment

The concept of peer empowerment was first introduced in 1997 by Olsson et al. (34) and since then a number of intervention on chronic diseases has been developed based on it. The empowerment of PL is reported to be capable of sustaining an evidence-based community-sustained nutrition and lifestyle behaviour intervention program for a large group of individuals residing within a close-knit community (35). The outlook of the peer support program is expected to be a low-in-cost thus sustainable prevention step in combating the rising prevalence of MetS due to its attempt to improve the concomitant lifestyle behaviour rather than focussing on any pharmacological approach (36). However, this empowerment of the peers will only be effective when peers acquired great understanding of the health message of the intervention materials thus can actively promote it within

and across their community as found in previous studies (37-39). Hence, PERSUADE is carefully designed to consider appropriate channel of intervention that is easily executed, intervention materials that used a common and simple language, lifestyle advices that is affordable and executable, and finally selection of program settings that are accessible and are familiar to and preferred by the target community (40).

### Applicability in Low-to-middle Income Population

The RCT of PERSUADE will be conducted in four low-to-middle class neighbourhoods in Johor which means the participants may be of a lower socioeconomic background than average Malaysians. This is not the exact representation of the entire population as the access to health providers, high quality food availability, health-supportive infrastructure and health knowledge levels are different in the urban as compared to the rural (41, 42). Hence, we are aiming for a better response in these areas due to a higher prevalence of MetS, absent of prevention measures and poor management among individuals with lower socioeconomic background (43). The applicability of peer support in these communities were shown to be well facilitated by the influence of lay health person, simplicity of health message, ability to collective set realistic health goals and the most important is that it is low in cost (43-45). Hence, it will be interesting to investigate responses from those with lower socio-economic status to a peer-led community health program. Eventually, PERSUADE can be an initiative peer support model to be implemented at the low socioeconomic community and suburban area for evaluation of its feasibility and cost-effectiveness. If successful, it can be a precursor for policy makers to initiate more rigorous promotion of such community peer-based programs to other parts of the country.

### Process Evaluation

Furthermore, PERSUADE combines the HBM concept in a peer support framework. The use of theoretical construct in this study allows the outcome evaluation to be supplemented by an adjunct process evaluation. The process evaluation will measure the degree of knowledge delivered and received, fidelity of acquired skills and its implementation as well as the participants' acceptability and satisfaction with the program. Similar to all peer-based interventions, this trial's reach is highly dependent on the participants' compliance based on the peer attendance rates and usability of PERSUADE materials. Collectively, these measures will enable us to resolve any enhancers and barriers of a peer-based program if the program were to be harnessed in other settings and context.

As a conclusion, PERSUADE is a three months community peer support nutrition and lifestyle behaviour peer support intervention for Malaysian adults with MetS. Peer support is a cost-effective, straightforward and sustainable measure to combat lifestyle-related diseases. Thus, a feasibility study among Malaysian adults is designed as RCT to elucidate its acceptance and effectiveness. As PERSUADE modules were theoretical, evidence-based and community-specific, the overall improvement in metabolic risk profile is greatly expected prior to nutrition and lifestyle behaviour improvement.

Table and Figures

Figure 1: Conceptual framework of PERSUADE peer support program

[figure not shown]

Figure 2: PERSUADE peer support program randomised controlled trial flow chart

[figure not shown]

Table 1: PERSUADE inclusion and exclusion criteria

Inclusion Criteria	Exclusion Criteria
Physically healthy men and women who are $\geq 18$ years old.	Pregnant, lactating or intend to become pregnant during the study period.
Literate with a fair command of Bahasa Melayu and/or English.	Diagnosed with Type 1 Diabetes Mellitus (T1DM)
Have been confirmed of having MetS according to Harmonised Criteria (46, 47).	Any predisposing condition compromising the quality of life or ability to participate according to protocol.
Willing to attend weekly peer gathering sessions.	Reported severe complications (chronic heart disease, cerebrovascular disease, diagnosed HIV/AIDS, cancer, emphysema, chronic liver or kidney disease) that would affect the participants' ability to follow the participation in peer activity.

Table 2: PERSUADE behavioural change matrix

No	Behavioural Theme	Behavioural Change Objectives	Delivery Approach	Self-efficacy Skills
1	MetS and its components	To understand MetS, its risk factors and disease severity.	An infographic to show the clustering of MetS components and premature death due to cardiovascular diseases	To be able to determine MetS based on the Harmonised criteria.
				To be able to measure waist circumference to detect abdominal obesity
2	Good Dietary Habit	To eat a variety of foods within your recommended intake.	An infographic to introduce Malaysian Food Pyramid and different classes of macronutrients	To be able to prepare meals according to "Pangan Sihat Malaysia" concept
		To prepare foods healthily with adequate amount of salt, sugars and condiments.	An infographic on daily serving sizes of main food class	To be able to estimate food quantity using household measures and palm estimation.
		To drink plenty of water daily.	An infographic on the importance of hydration	To be able to estimate the minimum amount of water required based on body weight
		To make effective use of nutrition information on food labels.	An infographic on Nutrition Information Panel and Food Health Claims	To be able to read and understand NIP hence to limit the intake of processed food
3	Cardiorespiratory Fitness	To be physically active every day.	An infographic on Physical Activity Pyramid	To be able to plan weekly workout schedule
		To understand physical inactivity and sedentary habits.	An infographic on sedentariness	To be able to incorporate movement in daily live (i.e. walking steps, stairs climb)

		To understand sleeping pattern and adequate rest.	An infographic on adequate sleeping pattern	To understand the importance of adequate rest and night sleep as well as naps in between
		To manage stress effectively	An infographic on everyday stress and its complications	To be able to acknowledge the presence of daily stress and seek help if necessary
4	Health Monitoring	To maintain body weight in a healthy range.	An infographic on BMI and Body Fat Percentage	To be able to calculate BMI and measure waist circumference
		To go for a blood screening every six week.	An infographic on good and bad cholesterol.	To have an increased awareness on how frequent to check blood pressure, lipid profile and fasting glucose
		To identify and set a personal health goals	An infographic on healthy life style	To be able to set realistic health goals in term of body weight, waist circumference and weekly diet and physical activity planning

Table 3: PERSUADE outcome assessment

Outcome	Instrument
Socio-demographic information	A brief sociodemographic questionnaire is use to collect basic details (i.e. age, marital status, ethnicity, educational status, occupation, personal and household income, family size and number of years of residence in current location).
Lifestyle characteristics	A brief questionnaire will inquire on participants' smoking habit, alcohol consumption and sleeping pattern. A validated health-related quality of life (HRQOL) questionnaire will be used to determine subject's fulfilment of life.
Physical Activity	International Physical Activity Questionnaire (IPAQ) will be used to determine the level of physical activity of the participants.
Anthropometry	A height scale, body tape and bio-impedance machine will be used to measure participants' height, weight, waist and hip circumferences and body composition.
Nutrition and diet	A semi-food frequency questionnaire (SFFQ) and 3 days 24H food recall will be used to record the participants' nutrients and dietary intake.
Blood biomaker	Finger prick rapid method will be used to detect participants' fasting blood sugar levels and fasting lipid profile.

